15.1 Sample size calculation

The sample size was estimated according to previous trials, with an expected between-group difference of 18 percentage points in favorable outcomes (90-day mRS 0-3, 81% in the NBO group, and 61% in the control group). We set the effective size to 0.25, α error probability to 0.05, power (1- β error probability) to 0.8, and the loss rate to 10%, the final result is that the total sample size is 154. However, the interim analysis showed the profound efficacy of NBO on ICH patients demonstrated by both imaging presentations and clinical evaluations. So, we terminated the trial ahead of schedule, and enrolled 96 participants (NBO group, 48 cases, and control group, 48 cases) at last.

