10.2.3 National Institute of Health Stroke Scale (NIHSS)

The NIHSS is commonly used to evaluate neurological deficits in stroke and comprises five items in 11 fields of different neurological statuses (scores range from 0–42, representing normal to severe neurological deficits). The NIHSS is scored at admission, 3-day, 7-day and 14-day after randomization during hospitalization.

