11.1 Efficacy outcomes

11.1.1 Primary outcome

Primary efficacy is independence at 90 days, as scored using the mRS, and dichotomized as a good (score 0-3) or a poor outcome (score 4-6), following the Cochrane analysis of thrombolysis in stroke. The proportion of patients in each arm with good outcomes is compared at 90 days.

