13.3 Follow-up periods

Neurological measurements including mRS score and Barthel index are assessed via a telephone interview at 90 days.

14. Adverse events monitoring

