15.2 Statistical methods

The modified intention-to-treat analysis of efficacy outcomes and safety outcomes were performed on the full analysis set, which was composed of all patients who received randomization independent of treatment and at least 1 efficacy evaluation after enrollment. The χ^2 test was used in the unadjusted analysis. A modified Poisson regression model with robust error estimation was used to analyze the primary outcome and other dichotomous endpoints, with adjustment for prespecified covariates (age, male and onset-to-needle time). Relative risk (RR) with a 95% confidence interval (CI) was calculated in both unadjusted and adjusted analyses. Generalized linear models (GLMs) were used to analyze continuous endpoints, including NIHSS scores, Barthel scale scores, and hematoma and edema volumes. The distribution of mRS was analyzed using an ordinal logistic regression model, and odds ratios (OR) with 95% CI were calculated. Post hoc subgroup analysis was performed for the primary outcome according to age, sex, and baseline NIHSS scores, with an OR of 95% CI. No interim analyses were performed.

A 2-sided P value <.05 is considered statistical significance. Because multiple comparisons potentially cause type I error, findings for secondary outcome analyses should be interpreted as exploratory. SPSS software (version 26, IBM) and R software (version 4.1.0) are used for the statistical analyses.

16. Data Management

The enrolled participants were entered in the case report form (CRF) by the evaluator within 24 hours and entered in the electronic form within 3 days. All of the entered personnel signed on the CRF. The assessors were blinded to allocation information. A data supervisor who was not involved in clinical research is set up for data verification. Two investigators who blinded to allocation information rechecked the original data, and if the data was found to be wrong, the data should be corrected in time. The data of modification and the person who modified it should be recorded to ensure that the data is correct.

17. Data and Security Monitoring Board (DSMB)

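### Section 15.1 gives an 18-point difference beside rates 20 points apart, an unlabelled effect size of 0.25, and a total of 154 that does not follow once the stated 10% loss is included

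*Combined protocol and SAP*

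**What the plan says.** Section 15.1 bases the sample size on a "difference of 18 percentage points in favorable outcomes (90-day mRS 0-3, 81% in the NBO group, and 61% in the control group". It continues: "We set the effective size to 0.25", and names neither the index nor a formula or software. With alpha 0.05 and power 0.8 it adds "and the loss rate to 10%, the final result is that the total sample size is 154". The same paragraph reports early termination: "So, we terminated the trial ahead of schedule, and enrolled 96 participants".

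Four other places bear on the calculation:

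- Section 15.2 fixes a two-sided 5% level, uses the chi-square test for the unadjusted analysis, and defines the full analysis set, "which was composed of all patients who received randomization independent of treatment and at least 1 efficacy evaluation after enrollment".
- Section 10.2.3 shows when an efficacy evaluation is first available: "The NIHSS is scored at admission, 3-day, 7-day and 14-day after randomization during hospitalization".
- Section 11.1.1 defines the primary comparison: "The proportion of patients in each arm with good outcomes is compared at 90 days".
- Section 13.3 says how the primary outcome is obtained: "Neurological measurements including mRS score and Barthel index are assessed via a telephone interview at 90 days".

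**The concern.** Three items in one short paragraph do not fit together. The stated difference disagrees with the two rates printed beside it. The 0.25 cannot be tied to those rates through w or h, the usual indices for proportions. The total of 154 is given as the end of a calculation that includes a 10% loss, yet it looks like a size before loss.

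Two things are at stake. A reader cannot tell which effect the trial was designed to detect, and cannot tell whether the stated loss was allowed for. If it was not, the 80% power claimed for 154 is overstated whenever lost patients drop out of the primary comparison. That can happen here: a patient enters the full analysis set on a day-3 score alone, the primary mRS comes from a telephone call at 90 days, and section 15.2 gives no rule for a missing 90-day mRS. The figure also remains in use, because 154 is the benchmark against which stopping at 96 is described.

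**Working it through.** **Inputs.** Rates 0.81 and 0.61, alpha 0.05, power 0.80, loss 10%, effect size 0.25 and total 154 (15.1); two-sided test (15.2); 1:1 allocation (7.4). Hence z = 1.960 and 0.842, and (1.960 + 0.842)² = 7.849. Loss is applied once, as N/0.9, rounded up.

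**1. The difference.** 81 − 61 = 20 points, not 18.

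**2. Reproducing 154.** Unpooled formula, per arm:

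n = 7.849 × (0.81×0.19 + 0.61×0.39) / 0.20² = 7.849 × 0.3918 / 0.04 = 76.88, so 77 per arm and **154 in total, before any loss**.

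**3. Other formulas, and the loss.** Pooled, with mean rate 0.71:

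n = (1.960×√0.4118 + 0.842×√0.3918)² / 0.04 = 79.62, so 80 per arm and 160 in total.

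| Formula, 81% v 61% | Evaluable | Enrolled (÷ 0.9) |
|---|---|---|
| Unpooled | 154 | 172 |
| Arcsine | 158 | 176 |
| Pooled | 160 | 178 |
| Continuity-corrected | 180 | 200 |

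Without continuity correction the shortfall against 154 is 172 − 154 = 18 to 178 − 154 = 24 patients, or 18/154 = 12% to 24/154 = 16%.

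**4. The 0.25.** For 81% v 61%:

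- w = 0.10/√(0.71×0.29) = 0.220
- h = 2·arcsin√0.81 − 2·arcsin√0.61 = 0.447

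The plan names no index, so each reading below is an assumption.

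| 0.25 read as | Evaluable | Enrolled | Power at 138 analysed |
|---|---|---|---|
| w (1 df) | 126 | 140 | 84% |
| f (two groups) | 128 | 143 | 83% |
| h | 504 | 560 | 31% |

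None gives 154 enrolled.

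**5. If 18 points was meant.** This needs a rate that the plan does not print, so the pairs are my assumption.

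| Pair | Evaluable (unpooled–pooled) | Enrolled |
|---|---|---|
| 81% v 63% | 188–194 | 209–216 |
| 79% v 61% | 196–202 | 218–225 |

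**6. Power delivered by 154.** With 10% lost, 154 × 0.9 = 138.6, taken as 69 per arm. For 81% v 61% at 69 per arm:

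- unpooled: Φ(0.20/√(0.3918/69) − 1.960) = Φ(0.694) = 0.756
- pooled: Φ((0.20 − 1.960×√(0.4118/69))/√(0.3918/69)) = Φ(0.645) = 0.740

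| Rates | 69 per arm | 77 per arm |
|---|---|---|
| 81% v 61% | 0.740–0.756 | 0.787–0.801 |
| 81% v 63% (assumed) | 0.656–0.671 | 0.705–0.719 |
| 79% v 61% (assumed) | 0.638–0.653 | 0.687–0.700 |

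For 81% v 61%, exact power of the chi-square test is 0.748 at 69 per arm and 0.791 at 77, inside these ranges.

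**The case against.** The best reply is that 154 has an obvious origin and the rest is loose wording. Both printed rates and the unpooled total point to a 20-point design, so 18 may be a slip. The 0.25 may be a relative difference: 20/81 = 0.247. Taken exactly, 0.81 × 0.75 = 0.6075, which needs 152 to 156 evaluable patients. On that reading 0.25 lacks only a label and contradicts nothing. Finally, the trial stopped at 96, so power at 154 describes a trial that was not completed, and no estimate or P value in 15.2 depends on it.

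Much of this is fair. The 20-point reading is the more plausible one, the 18-point figures rest on rates I had to supply, and 0.25 is not shown to be wrong, only unidentified. But the plan states none of these explanations. Other routes also land on or near 154: w = 0.25 inflated twice (126/0.9 = 140, then 140 × 1.1 = 154), or w = 0.25 with 2 degrees of freedom (154.2 before loss), which does not fit a two-by-two table. The most natural route leaves out the 10% loss that the sentence lists. Early stopping limits the consequence but does not correct the paragraph.

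**Conclusion.** The concern holds. The 18 v 20 point conflict is certain and needs no assumption. The 0.25 is unidentified and is neither w nor h for the printed rates. As a total after 10% loss, 154 does not follow: at two-sided 0.05 and 80% power, 81% v 61% needs 172 to 178 enrolled (unpooled to pooled, loss applied once). It does match the unpooled size with no loss added, though the plan does not say that it was derived that way.

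Whether the 80% target is met at 154 depends on a point the plan leaves open. For 81% v 61% it is missed, at about 74 to 76%, if lost patients have no 90-day mRS; it is roughly met, at about 79 to 80%, if all 154 are analysed. The paragraph should be corrected. The defect lies in the stated design basis and does not by itself invalidate the analysis.

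**What to change.** Add a dated clarification to section 15.1 that:

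1. reconciles the 18-point difference with the two rates, from the source used at design;
2. names the index behind 0.25, or replaces it with the two proportions;
3. states the formula that gave 154 and how the 10% loss entered it;
4. keeps 0.8 as the design target and adds the power that 154 delivers under the reconciled rates after the stated loss, saying whether patients lost before day 90 are analysed;
5. notes that the 0.8 refers to the planned 154 and not to the 96 enrolled. It should give no power figure for 96; interpretation should rest on the relative risk and 95% CI in section 15.2.

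The cost is text only: no patients, data, estimate, test or error rate changes. The delivered power in item 4 will read slightly below target if 81% v 61% is confirmed and lost patients are not analysed.

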A Data and Security Monitoring Board (DSMB) was established in this study in order to ensure the integrity of the trial and protect the rights and health of subjects. During the study period, regular monitoring visits will be made to the clinical site to ensure that all procedures were complied with the approved protocol/amendment. The safety and efficacy of the interventions were assessed at interim time-point and DSMB had the authority to terminate the trial.

18. Ethical Considerations

The study protocol was approved by the Institutional Ethics Committee (EC) of the Affiliated Hospital of Jiujiang University (Jiujiang, China, 2020001) in accordance with the guidelines of the 1964 Declaration of Helsinki. All participants or their legally authorized representative provided written informed consent.

Modify the protocol: The research agreement must be strictly followed. The revised research agreement must be approved by the ethics committee, and the revised research agreement can be implemented after approval.

Protocol adherence: Prior to beginning the study, the Investigator must sign the Investigator Agreement and Signature page documenting his/her agreement to conduct the study in accordance with the protocol. An Investigator must not make any changes or deviate from this protocol, except to protect the life and physical well-being of a subject in an emergency. Each deviation from the protocol must be documented with the date and reason for the deviation and reported to EC as soon as possible.

Written informed consent form: The informed consent Form (ICF) document should be translated into a language that the subject can understand. The informed consent must be approved by the ethics committee before use. ICF must agree with the current Good Clinical Practice (GCP) guidelines and the Declaration of Helsinki. Before participating in a clinical trial, each subject or its legally authorized representative (LAR) must understand the content of the informed consent form and sign it. The informed consent should clearly indicate the rights and obligations of the subjects. The written informed consent must be properly recorded with the signature of the person or LAR. The consent process must be recorded in the subject's medical record.

References

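### Sections 15.1 and 17 report an interim look at efficacy, and 15.1 a stop at 96 of 154, but 15.2 denies any interim analysis and tests at an unadjusted P<.05, so a 5% type I error is not shown

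*Combined protocol and SAP*

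**What the plan says.** Three sections of the combined protocol and SAP bear on this.

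- **Section 15.1 (sample size)** sets a total of 154, then reports: "However, the interim analysis showed the profound efficacy of NBO on ICH patients demonstrated by both imaging presentations and clinical evaluations". It continues: "So, we terminated the trial ahead of schedule, and enrolled 96 participants", with 48 in each arm.
- **Section 17 (DSMB)** says: "The safety and efficacy of the interventions were assessed at interim time-point and DSMB had the authority to terminate the trial".
- **Section 15.2 (statistical methods)** says: "No interim analyses were performed". It sets the criterion "A 2-sided P value <.05 is considered statistical significance" and, for the primary and other binary outcomes, "Relative risk (RR) with a 95% confidence interval (CI) was calculated in both unadjusted and adjusted analyses".

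The only remark on multiplicity, also in 15.2, is that "findings for secondary outcome analyses should be interpreted as exploratory". It does not deal with interim looks. The primary comparison (11.1.1) is of 90-day mRS 0-3: "The proportion of patients in each arm with good outcomes is compared at 90 days". The imaging measures are secondary outcomes (11.1.2).

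**The concern.** A reader who follows 15.2 will take the primary P value, relative risk and interval as coming from a fixed-sample trial with a 5% type I error. Section 15.1 describes something else: enrolment ended because accumulating efficacy results looked good. Repeated testing at an unadjusted .05 raises the chance of a false positive, and estimates from trials that stop on a favourable primary result run high on average.

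The text gives no means of judging how far either applies here. It does not state the rule, how many looks there were or when, which endpoint triggered the stop, or how many patients had reached 90 days at the look. Part of the stated ground for stopping is imaging, which belongs to the outcomes that 15.2 calls exploratory. It is also unclear who decided: section 17 gives the DSMB the authority, while 15.1 is written in the first person plural.

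**Working it through.** **1. The statements side by side.** Section 15.1: an interim analysis took place, showed efficacy, and led to the stop. Section 17: efficacy was assessed at an interim time-point. Section 15.2: no interim analysis took place. All three are current text, and 15.2 cannot hold together with the other two. This step needs no assumption.

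**2. Inputs for the illustrations.** From 15.1: 154 planned, 96 enrolled (48 per arm), 81% v 61% with a good outcome. From 15.2: two-sided .05. Assumed, because not given: one look, at the primary outcome, with all 96 patients, so that the information fraction is t = 96/154 = 0.623. The 96 is final enrolment and is not shown to be the number analysed at the look.

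**3. Type I error.** The plan's own figure, for a single final test, is 2.5% + 2.5% = 5%. With one look, let Z1 and Z2 be the interim and final statistics, with correlation √0.623 = 0.79 under no effect. Section 15.1 describes a stop for benefit, so:

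- Favourable tail = 1 − P(Z1 ≤ c, Z2 ≤ 1.96). With c = 1.96 this is 3.9% instead of 2.5%.
- Unfavourable tail = P(Z1 ≤ c, Z2 < −1.96) = 2.5%.
- Total = 3.9% + 2.5% = 6.4%.

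| Assumed rule (final test two-sided .05) | Total type I error |
|---|---|
| One look at t = 0.623, stop for benefit at P<.05 | 6.4% |
| Same, stopping in either direction | 7.9% |
| Look at t = 0.25 to 0.75, stop for benefit at P<.05 | 7.0% to 6.2% |
| Look at t = 0.623, stop for benefit at P<.013 | 5.2% |
| Look at t = 0.623, stop for benefit at P<.001 | 5.0% |
| Looks at 48, 96 and 154, stop for benefit at P<.05 (simulation) | 7.9% |

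**4. Estimate after a stop.** Take the truth as 81% v 61%, which is 20 points. (Section 15.1 also states 18 points; that mismatch is a separate matter.) The test is the uncorrected chi-square.

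- Trials that stop for benefit at 48 per arm with P<.05: mean estimate 25.9 points. The probability of stopping is 0.595.
- Fixed trials of 77 per arm that reach P<.05: mean estimate 22.6 points. This is the planned design's own significance filter.
- Excess over that filter: 25.9 − 22.6 = 3.3 points.
- Average over all trials, stopped or not: the mean at 48 per arm is 20, so trials that continue average (20 − 0.595 × 25.88)/0.405 = 11.4 at the look. With 29 more per arm they average (48 × 11.36 + 29 × 20)/77 = 14.6. The overall mean is 0.595 × 25.88 + 0.405 × 14.6 = 21.3 points.

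For stopping at P<.05, .013 or .001, the mean among stopped trials is 25.9, 29.0 or 34.7 points, while the mean over all trials is 21.3, 21.3 or 20.7. A stricter rule therefore raises the overestimate only among trials that stop.

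**5. If imaging drove the stop.** Using a normal approximation with an SE of 0.0903 for the difference and an assumed mean imaging Z of 2.21 at 96, with stopping at imaging P<.05, the mean primary estimate is 20.0, 22.9 or 24.1 points for a correlation of 0, 0.5 or 0.7 with the primary outcome. With no correlation there is no bias.

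**The case against.** The strongest defence is that 15.2 means no formal, preplanned interim analysis, and that a DSMB review under section 17 is ordinary oversight. That does not reconcile the text: 15.1 itself speaks of an interim analysis and gives its efficacy result as the reason for stopping. Nor does the proof-of-concept label in the introduction remove the problem, since the plan names a primary efficacy outcome and a significance threshold.

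Other objections do stand, and they limit the point.

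- **Size of the inflation.** A reader might infer that the trial ran at 7.9% or more. The 7.9% for a single look counts stops in either direction, whereas 15.1 describes stopping only for benefit. Under a strict rule the inflation would be close to nil.
- **Size of the bias.** A reader might attribute the whole 5.9 points (25.9 − 20) to early stopping. A fixed trial of 96 with no look, taken only when P<.05, gives the same 25.9. Against the planned 154, the excess is about 3.3 points.
- **Certainty of the bias.** A reader might infer that the estimate must be too high. The trigger is not stated, and a stop driven by imaging unrelated to the mRS would leave the estimate unbiased.
- **Who stopped the trial.** A reader might infer that the investigators bypassed the DSMB. The two passages are compatible, since investigators may act on a DSMB decision. This is an ambiguity, not a contradiction.

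**Conclusion.** The point holds. Sections 15.1 and 17 contradict 15.2 on whether efficacy was looked at before the end, and the primary inference in 15.2 rests on the statement in dispute. With no boundary or account of the looks, control of type I error at 5% is not shown. The documents do not establish that it was exceeded, or by how much.

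The figures are illustrations under the assumptions stated, not bounds. With stopping for benefit, total type I error runs from 5.0% under a strict single-look threshold to 7.9% for three looks at .05, with 6.4% for one look at 96/154. For a true difference of 20 points, the mean estimate after a stop at P<.05 is 25.9, against 22.6 under the planned design's own significance filter. The contradiction and the missing rule need correcting whichever scenario applies.

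**What to change.** Reconcile 15.1, 15.2 and 17, and correct or delete the sentence in 15.2 that denies interim analyses so that it matches what was done. State the number and timing of looks, the number of patients with a 90-day mRS at each, the endpoints seen, who decided to stop, and by what rule.

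- **If a boundary was set before the look:** judge the primary outcome against it and report a stopping-adjusted P value, confidence interval and relative risk. State the method and how any patients accrued after the look are handled.
- **If none was set:** say that the primary P value and interval are nominal, that they are not shown to control type I error at 5%, and that the effect estimate may be biased upward by early stopping, to a degree that depends on what triggered the stop.

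A boundary chosen afterwards must not be used to support the primary claim; it may appear only as a labelled sensitivity comparison.

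The cost is wording, plus one extra analysis only if a boundary was preset. That analysis requires a choice of adjustment method and possibly overrun handling. The primary claim becomes less favourable. No more patients are needed.

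### The stated power of 0.8 belongs to a planned total of 154; enrolment ended at 96, and no power, precision or stopping design is written for that number

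*Combined protocol and SAP*

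**What the plan says.** Section 15.1 gives the design rates as "90-day mRS 0-3, 81% in the NBO group, and 61% in the control group", although it words the difference as "with an expected between-group difference of 18 percentage points in favorable outcomes". It adds "We set the effective size to 0.25", without naming the metric, and "α error probability to 0.05". The only power statement is "power (1- β error probability) to 0.8, and the loss rate to 10%, the final result is that the total sample size is 154".

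The same paragraph then says that an interim analysis showed efficacy, and continues: "So, we terminated the trial ahead of schedule, and enrolled 96 participants (NBO group, 48 cases, and control group, 48 cases) at last". No power, detectable difference or expected precision follows for 96.

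Section 15.2 describes a single comparison at two-sided P<.05. For the primary outcome it names a modified Poisson model giving an RR with 95% CI, and for the simpler comparison "The χ^2 test was used in the unadjusted analysis". It also states "No interim analyses were performed". Section 17 says the opposite: safety and efficacy were assessed at an interim time-point, and the monitoring board could end the trial. None of the three sections gives a boundary, an alpha-spending rule or the timing of a look.

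**The concern.** A power figure belongs to a procedure: a sample size, a test, an alpha and any stopping rule. Section 15.1 gives 0.8 for one procedure (154 patients), and the trial reports the result of another (96 patients, stopped for a reason that 15.1 and 15.2 dispute). Nothing written carries the 0.8 across.

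The practical stake is interpretation. A significant result from a small or early-stopped sample tends to exaggerate the effect, and 15.1 already describes the efficacy in strong terms. Non-significant adjusted or subgroup results at 96 also cannot be read as if they had 80% power behind them.

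**Working it through.** **Inputs.** From 15.1: 81% v 61%, a stated difference of 18 points, alpha 0.05, power 0.8, 10% loss, planned total 154, enrolled 48 + 48. From 15.2: two-sided test, chi-square and RR. From 7.4: 1:1 allocation.

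**1. The plan's own figure.** With unpooled variance, n per arm = (1.960 + 0.842)² × (0.81×0.19 + 0.61×0.39) / 0.20² = 7.849 × 0.3918 / 0.04 = 76.9, so 77 per arm and 154 in total. This matches, but only with no allowance for loss; dividing by 0.9 gives 171.1, so 172. Power at 77 per arm is 80.1% (unpooled), 78.7% (pooled) or 79.1% (exact enumeration of the uncorrected chi-square). So 0.8 fits 154 evaluable patients. The missing loss allowance is a separate matter.

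**2. 96 as a fixed sample (the account in 15.2).** At 48 per arm:
- Unpooled: SE = √(0.3918/48) = 0.0903; power = Φ(0.20/0.0903 − 1.960) = Φ(0.254) = 60.0%.
- Pooled: null SE = √(2×0.71×0.29/48) = 0.0926; power = Φ((0.20 − 1.960×0.0926)/0.0903) = Φ(0.204) = 58.1%.

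| Case | Power |
|---|---|
| 81% v 61%, 48 per arm, uncorrected chi-square (pooled, exact, unpooled) | 58.1%, 59.4%, 60.0% |
| Same, unadjusted Wald test of log RR | 56.7% |
| Same rates, 10% loss (43 per arm), uncorrected chi-square | 53-55% |
| 18 points (79% v 61% or 81% v 63%), 48 per arm, uncorrected chi-square | 49-52% |
| Effect size 0.25 read as Cohen's w, N = 96 | 68.8% |

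The documents do not say which rate is off if 18 points is right, so both options are shown. The last row is the most generous reading. However, 81% v 61% gives w = 0.10/√(0.71×0.29) = 0.220, not 0.25. Every reading is below 0.8.

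For 80% power at 48 per arm against 61%, the NBO rate must be about 85.5-86%, a difference of about 25 points.

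**3. An unadjusted look at 96, then 154 (the account in 15.1 and 17).** The documents give neither the number nor the timing of looks. The assumption here is one look at 48 per arm and a final test at 77 per arm, each by uncorrected chi-square at two-sided 0.05. Simulation gives 81.6% rejection at either look under 81% v 61%. With equal rates in the two arms, it gives about 8% rejection.

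**4. Size of the estimate, given significance at 96.** Under a true 81% v 61%, the mean observed difference among results significant in favour of NBO (exact enumeration, uncorrected chi-square) is 25.9 points, an excess of 25.9 − 20 = 5.9. This conditions only on significance at 48 per arm, so it applies under step 2 and step 3 alike.

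**5. Dependence on the test.** With 29/48 in control, 38/48 in NBO (18.75 points) gives chi-square P=.045 but RR Wald P=.051. On the RR scale, 39/48 (20.8 points) is needed. No single threshold for significance holds for both tests named in 15.2.

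**The case against.** The strongest reply is that nothing in 15.1 is false. It attaches 0.8 to 154, then openly reports the early stop and the 96; it never claims 80% power for 96. That stands. The defect is that nothing is restated for the number used, not that a figure is miscalculated for it.

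The second reply is that power at a fixed 96 does not describe a trial that stopped because a look was positive; had the look been negative, enrolment would presumably have gone on towards 154. That also stands if 15.1 and 17 are right. A reader might infer from the 57-60% that a true 20-point effect would have been missed about 4 times in 10. The documents do not support this unconditionally: it holds only if 96 was a fixed sample, which 15.1 contradicts. The alternative does not rescue the stated design either, since its 82% comes with about 8% type I error instead of 5%.

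Third, after a trial has ended the CI conveys precision better than a power figure, 15.2 already provides one, and it labels secondary results exploratory and subgroups post hoc. This is fair and limits the consequence. It does not remove the need to say that the estimate comes from a stopped trial and probably exaggerates.

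Finally, the fixed-sample figure is for unadjusted tests with all 96 evaluable. The full analysis set in 15.2 could be smaller, and the power of the covariate-adjusted model cannot be computed from the documents.

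**Conclusion.** The point holds in limited form and should be addressed. Power 0.8 at two-sided 0.05 is not a property of the procedure that produced the 96-patient result, whichever account of the interim look is true:

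- No interim look: about 57-60% for 81% v 61%, about 53-55% with 10% loss, and about 50% for 18 points.
- Unadjusted look at 96 before 154: about 82% chance of rejection, with about 8% type I error.

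On both accounts, a significant result at 96 overstates a true 20-point difference by about 6 points on average. This rests on the plan's own rates, an uncorrected chi-square and, for the two-look figures, the assumed single look at exactly 96. If the true difference is not 20 points, the overstatement will differ.

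The documents do not support saying that the plan claims 80% power for 96, or that the result is invalid because of its size. The uncontrolled type I error of an undescribed look is the graver problem and needs its own answer.

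**What to change.** 1. Reconcile 15.1, 15.2 and 17 on whether an interim look took place. If it did, report when, how many looks, on which outcomes and by what criterion. If it did not, correct the reason for stopping in 15.1.
2. In 15.1, say that 0.8 refers to the planned 154 only.
3. Give the figure for 96 with its label: fixed-sample, unadjusted, all 96 evaluable, two-sided 0.05, power about 57-60% for 81% v 61%, with 80% only for a difference of about 25 points. If a look is confirmed, say that this figure does not describe the whole procedure.
4. With the primary result, state that the RR and its 95% CI come from a trial that 15.1 reports as stopped early for efficacy, are likely to overstate the effect, and are preliminary.

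Do not add patients. The cost is a few sentences in 15.1 and in the interpretation of the primary result, with no new data. The downside is a less favourable stated power and a more cautious conclusion.
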